4.1.2. Handling of Dropouts or Missing Data

All analyses and descriptive summaries will be based on the observed data. Unless otherwise specified, missing data will not be imputed or "carried forward." Rules for handling dropouts or missing data are listed by type of analysis alphabetically.

- Adverse event (AE) or concomitant therapy:
 - The missing day of onset of an AE or start date of a concurrent therapy will be set to
 - first day of the month that the event occurred, if the onset yyyy-mm is after the yyyy-mm of first study treatment;
 - the day of the first study treatment, if the onset yyyy-mm is the same as yyyy-mm of the first study treatment; or
 - the date of informed consent, if the onset yyyy-mm is before the yyyy-mm of the first treatment.
 - The missing day of resolution of an AE or end date of a concurrent therapy will be set to
 - the last day of the month of the occurrence. If the patient died in the same month, then set the imputed date as the death date.
 - If the onset date of an AE or start date of a concurrent therapy is missing both the day and month, the onset date will be set to
 - 01 January of the year of onset, if the onset year is after the year of the first study treatment;
 - the date of the first treatment, if the onset year is the same as the year of the first study treatment; or
 - the date of informed consent, if the onset year is before the year of the first treatment.

- If the resolution date of an AE or end date of a concurrent therapy is missing both the day and month, the date will be set to:
 - 31 December of the year of occurrence. If the patient died in the same year, then set the imputed date as the death date.
- If the date is completely missing, then no imputation will be done and the event will be considered as treatment emergent with unknown onset date, unless the end date rules out the possibility.
- Diagnosis date, the following conventions will be used for imputing partial dates:
 - If only the day of the month is missing, the 15th of the month will be used to replace the missing day.
 - If both the day and the month are missing, "Jul 1" will be used to replace the missing information.
- General rule for imputing other dates (excluding the dates used in the efficacy analyses):
 - If only the day is missing, then assign Day 15 of the month, or the date of death if the patient died prior to 15th of the same month to the day.
 - If month is missing, then the date will be set to July 1 of the year, or the date of death if the patient died prior to July 1 of the same year.

However, in all cases, after imputation, check if the imputed date is logically consistent with other relevant date variable(s) and make appropriate correction if necessary.

• Time-to-event analysis: all censored data will be accounted for using appropriate statistical methods. This information will be copied directly from the protocol. Additional general considerations may be added.

4.2. Participant Dispositions

A detailed description of patient disposition will be provided, including a summary of the number and percentage of participants enrolled (i.e., randomized) in the study, and treated as well as number and percentage of participants completing the study, defined as the participants who are evaluable for the primary endpoint, or discontinuing the study (overall and by reason for discontinuation). Reasons for the screen failures will also be summarized.

4.3. Primary Endpoint Analysis

4.3.1. Definition of Endpoint

The primary endpoint is investigator-assessed PFS. PFS is defined as the time from randomization to the date of first documented progression of disease or death from any cause in the absence of disease progression using Response Evaluation Criteria in Solid Tumors (RECIST) version 1.1 criteria (Eisenhauer et al. 2009). Participants known to be alive and without disease progression will be censored according to the censoring scheme detailed in Section 4.3.2.

4.3.2. Main Analytical Approach

The Kaplan-Meier method (Kaplan and Meier 1958) will be used to estimate the PFS curves. Median PFS and PFS rates at various time points with 95% CIs will be estimated for each arm. The comparison of PFS curves between treatment arms will be conducted by a stratified log-rank test as the primary analysis, stratified by the randomization strata. The treatment effect will be estimated by hazard ratio with its corresponding 95% CIs using the stratified Cox proportional hazard model (Cox 1972) with treatment as the only covariate, stratified by the randomization strata. A detailed PFS event/censoring scheme is provided in the table below.

PFS Censoring Scheme

Situation	Event/Censor	Date of Event or Censor
Tumor progression or death	Event	Earliest date of PD or death
		Date of last adequate tumor assessment,
No tumor progression and no death	Censored	per RECIST 1.1 criteria, or date of
		randomization (whichever is later)
	Unless	
No baseline radiologic tumor assessment available	Censored	Date of randomization
No adequate postbaseline tumor assessment		
available and death reported after 2 scan intervals	Censored	Date of randomization
following randomization		
		Date of last adequate tumor assessment,
New systemic anticancer therapy prior to tumor	Censored	per RECIST 1.1 criteria, prior to start of
progression or death		new therapy or date of randomization
		(whichever is later)
Tumor progression or death documented		Date of last adequate tumor assessment
immediately after 2 or more missing scan intervals	Consorad	prior to 2 or more missing scans, per
following last adequate tumor assessment or	Censored	RECIST 1.1 criteria, or date of
randomization (whichever is later)		randomization (whichever is later)

Abbreviations: PD = progressive disease; RECIST 1.1 = Response Evaluation Criteria in Solid Tumors, version 1.1.

^a Symptomatic deterioration (that is, symptomatic progression that is not radiologically confirmed per RECIST 1.1 criteria) will not be considered as tumor progression.

- ^b Adequate tumor assessment per RECIST 1.1 criteria refers to an assessment with 1 of the following responses: CR, PR, SD, or PD.
- ^c The 2-scan interval is counted from the date of last adequate tumor assessment to the date of next 2 scheduled tumor assessments plus 8 days (adjusted by tumor assessment window).
- ^d If there are multiple dates associated with 1 assessment, the assessment date will be set to the first date when the overall response is PD and the last date otherwise.

For the primary objective of PFS for Arm A versus Arm B in the ITT population, one interim PFS analysis will be conducted when approximately 192 (40% information fraction) investigator-assessed events have been observed in Arm A and Arm B, and the final PFS analysis will be conducted when approximately 480 investigator-assessed events have been observed in the same population. The interim analysis will allow the trial to stop early due to futility.

For the primary objective of PFS for Arm A versus Arm B in the *ESR1*-mutation detected population, the final analysis will be conducted when approximately 192 investigator-assessed events have been observed in the *ESR1*-mutation detected subset. The comparison of PFS curves

between treatment arms will be conducted by a stratified log-rank test as the primary analysis, stratified by the randomization strata, excluding region. Region is excluded in the stratified analysis for the subset to reduce the number of strata from 12 to 4. The treatment effect will be estimated by hazard ratio with its corresponding 95% CIs using the stratified Cox proportional hazard model with treatment as the only covariate. Similarly, region will be excluded in the stratified analysis.

For the primary objective of PFS for Arm C versus Arm A in the ITT population, 1 interim PFS analysis will be conducted when approximately 100 events have been observed among the approximately 440 participants concurrently randomized to Arm A and Arm C. This interim analysis will allow the trial (Arm A versus Arm C comparison) to stop early due to futility. The final analysis will be conducted when approximately 248 events have been observed among the participants concurrently randomized to both arms. The PFS between Arm C and Arm A will only be tested hierarchically based on the graphical approach.

See further details about the interim analyses in Section 4.9.3.

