 - Non-measurable bone-only disease. Non-measurable bone-only disease may include any of the following:
 - i. Blastic bone lesions (also known as sclerotic bone lesions)
 - ii. Lytic bone lesions without a measurable soft tissue component
 - iii. Mixed lytic-blastic bone lesions without a measurable soft tissue component
- 9. Have a Performance Status of 0 or 1 on the Eastern Cooperative Oncology Group scale (Oken et al. 1982)

10. Have adequate organ function as defined in table below

System	Laboratory Value
Renal	·
Serum creatinine or,	<1.5× ULN OR
Measured creatinine clearance or,	≥50 mL/min
Calculated creatinine clearance	(See Section 10.5 Appendix 5)
Hematologic	
ANC	$\geq 1.5 \times 10^{9}/L$
Platelets	$\geq 100 \times 10^{9}/L$
Hemoglobin	≥9 g/dL

Note: transfusions to increase a patient's hemoglobin level or initiation of erythropoietin or G-CSF therapy to meet enrollment criteria are not allowed in the 14 days preceding the first dose of study drug.

Hepatic	
	≤1.5× ULN
Total bilirubin	(Patients with Gilbert's syndrome with a total bilirubin ≤ 2.0 times ULN and
	direct bilirubin within normal limits are permitted.)
ALT and AST	≤3× ULN

Abbreviations: ALT = alanine aminotransferase; ANC = absolute neutrophil count; AST = aspartate aminotransferase; G-CSF = granulocyte colony stimulating factor; ULN = upper limit of normal.

- 11. Have discontinued previous therapies for cancer prior to receiving study drug, and recovered from the acute effects of therapy to at least Grade 1, except for residual alopecia and peripheral neuropathy, with the following therapy washout periods required prior to receiving study drug:
 - a. for myelosuppressive agents (for example, CDK4/6 inhibitors): at least 21 days
 - b. for nonmyelosuppressive agents (for example, Endocrine Therapy): 7 days or 5 half-lives, whichever is shorter
 - c. for investigational agents: 28 days or 5 half-lives, whichever is shorter
- 12. Patients must be able to swallow capsules/tablets
- 13. Are willing to participate for the duration of the study and to follow study procedures
- 14. Capable of giving signed informed consent as described in Section 10.1 Appendix 1, which includes compliance with the requirements and restrictions listed in the informed consent form (ICF) and in this protocol.

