8.1.3. Primary Efficacy Measure

Response Evaluation Criteria in Solid Tumors v1.1 (Eisenhauer et al. 2009; Section 10.3 Appendix 3) will be applied as the primary criteria for assessment of tumor response and date of tumor progression. The method of tumor assessment used at baseline must be used consistently throughout the study. Local tumor imaging (investigator assessment with site radiological reading) will be used.

Sponsor or its designee will collect and store all tumor assessment images on all randomized participants throughout the study to permit a blinded independent central review of patient scans. Please see the Site Imaging Manual for guidelines on how the various imaging studies should be performed.

The PFS time is measured from the date of randomization to the date of first objective progression or the date of death due to any cause, whichever is earlier. For those patients with nonmeasurable bone-only disease (refer to Inclusion Criterion [8]), objective progression will be established if at least 1 of the following criteria is met:

- the appearance of 1 or more new lesions (in bone or outside of bone), or
- unequivocal progression of existing bone lesions.

According to RECIST v1.1, the finding of a new lesion should be unequivocal and not attributable to findings thought to represent something other than tumor (for example, some "new" bone lesions may be simply healing or flare of preexisting lesions). Pathologic fracture, new compression fracture, or complications of bone metastases will not be considered as evidence of disease progression, unless at least 1 of the above criteria is met.

See Section 9.4.3 for definitions of the efficacy endpoints.

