9.4.3. Efficacy Analyses

9.4.3.1. Primary Analyses

The primary endpoint is investigator-assessed PFS. PFS is defined as the time from randomization to the date of first documented progression of disease or death from any cause in the absence of disease progression using RECIST version 1.1. Participants known to be alive and without disease progression will be censored at the last known date of progression-free assessment. A detailed PFS event/censoring scheme is provided in the table below. The Kaplan-Meier method (Kaplan and Meier 1958) will be used to estimate the PFS curves. Median PFS and PFS rates at various time points with 95% CIs will be estimated for each arm. The comparison of PFS curves between treatment arms will be conducted by a stratified log-rank test as the primary analysis, stratified by the randomization strata. The treatment effect will be estimated by hazard ratio with its corresponding 95% CIs using the stratified Cox proportional hazard model with treatment as the only covariate, stratified by the randomization strata.

For the primary objective of PFS for Arm A versus Arm B in the ITT population, 1 interim PFS analysis is planned when approximately 192 investigator-assessed events have been observed to allow the trial to stop early due to futility, and the final analysis will be conducted when approximately 480 investigator-assessed events have been observed in the same population. Details about the interim analysis are provided in Section 9.5.

For the primary objective of PFS for Arm A versus Arm B in the *ESR1*-mutation detected population, the final analysis will be conducted when approximately 192 investigator-assessed events have been observed. The comparison of PFS curves between treatment arms will be conducted by a stratified log-rank test as the primary analysis, stratified by the randomization strata. The treatment effect will be estimated by hazard ratio with its corresponding 95% CIs using the stratified Cox proportional hazard model with treatment as the only covariate. Strata may be collapsed to reduce the number of strata for the primary analysis. More details will be provided in the SAP.

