Progressive Disease (PD): at least a 20% increase in the sum of the diameters of target lesions, taking as reference the smallest sum on study (including the baseline sum if that is the smallest). In addition to the relative increase of 20%, the sum must also demonstrate an absolute increase of at least 5 mm. The appearance of 1 or more new lesions is also considered progression.

For equivocal findings of progression (for example, very small and uncertain new lesions; cystic changes or necrosis in existing lesions), treatment may continue until the next scheduled assessment. If at the next scheduled assessment, progression is confirmed, the date of progression should be the earlier date when progression was suspected.

Stable Disease (SD): neither sufficient shrinkage to qualify for PR nor sufficient increase to qualify for PD, taking as reference the smallest sum diameters while on study.

Not Evaluable: when an incomplete radiologic assessment of target lesions is performed or there is a change in the method of measurement from baseline that impacts the ability to make a reliable evaluation of response.

Evaluation of Nontarget Lesions

Complete Response: disappearance of all nontarget lesions and normalization of tumor marker level. All lymph nodes must be non-pathological or normal in size (<10 mm short axis).

Non-CR/ non-PD: persistence of 1 or more nontarget lesions and/or maintenance of tumor marker level above the normal limits.

Progressive Disease: unequivocal progression of existing nontarget lesions. The appearance of 1 or more new lesions is also considered progression.

Not Evaluable: when a change in method of measurement from baseline occurs and impacts the ability to make a reliable evaluation of response.

Evaluation of Best Overall Response

The best overall response is the best response recorded from the start of the study treatment until the earliest of objective progression or start of new anticancer therapy, taking into account any requirement for confirmation. The patient's best overall response assignment will depend on the findings of both target and nontarget disease and will also take into consideration the appearance of new lesions. The Best Overall Response will be calculated via an algorithm using the assessment responses provided by the investigator over the course of the trial.

Time Point Response

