It is assumed that at each protocol-specified time point, a response assessment occurs (when no imaging/measurement is done at all at a particular time point, the patient is not evaluable (NE) at that time point). Table 1 provides a summary of the overall response status calculation at each time point for patients who have *measurable disease* at baseline.

Target Lesions	Non-Target Lesions	New Lesions	Overall Response
CR	CR	No	CR
CR	Non-CR/non-PD	No	PR
CR	Not evaluated	No	PR
PR	Non-PD or not all evaluated	No	PR
SD	Non-PD or not all evaluated	No	SD
Not all evaluated	Non-PD	No	NE
PD	Any	Yes or No	PD
Any	PD	Yes or No	PD
Any	Any	Yes	PD

Table 2: Time Point Response: Patients with Target (± Nontarget) Disease

Abbreviations: CR = complete response; NE = not evaluable; PD = progressive disease; PR = partial response; SD = stable disease.

Table 3 is to be used when patients have *nonmeasurable* disease only.

Nontarget Lesions	New Lesions	Overall Response	
CR	No	CR	
Non-CR/non-PD	No	Non-CR/non-PD ^a	
Not all evaluated	No	NE	
Unequivocal PD	Yes or No	PD	
Any	Yes	PD	

Table 3: Time Point Response: Patients with Nontarget Disease Only

Abbreviations: CR = complete response; NE = not evaluable; PD = progressive disease.

^a non-CR/non-PD is preferred over SD for nontarget disease.

Frequency of Tumor Reevaluation

A baseline tumor evaluation must be performed within 4 weeks before patient begins study treatment. Frequency of tumor reevaluation while on and adapted to treatment should be protocol specific and adapted to the type and schedule of treatment. In the context of Phase 2 studies where the beneficial effect therapy is not known, follow-up every 6-8 weeks is reasonable. Normally, all target and non-target sites are evaluated at each assessment using the same method. However, bone scans may need to be repeated only when CR is identified in target disease or when progression in bone is suspected.

Confirmatory Measurement/Duration of Response

Confirmation

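### The definition of an adequate tumor assessment leaves out non-CR/non-PD, so read literally it censors event-free patients with non-measurable bone-only disease at randomization

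*SAP*

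**What the plan says.** Footnote b of the PFS censoring table is the same in SAP 4.3.2 and Protocol 9.4.3.1: "Adequate tumor assessment per RECIST 1.1 criteria refers to an assessment with 1 of the following responses: CR, PR, SD, or PD". For a patient with no progression and no death, the table sets the censoring date at the last adequate assessment or at randomization, whichever is later. The row for new systemic therapy before progression has the same fallback.

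Protocol 5.1, criterion 8, admits patients without measurable disease if their disease is confined to bone ("Non-measurable bone-only disease may include any of the following", followed by blastic, lytic and mixed lesions). Protocol 8.1.3 gives them a separate rule, under which "objective progression will be established if at least 1 of the following criteria is met". Table 3 of Protocol Appendix 3 covers nontarget disease only. Its possible outcomes are CR, non-CR/non-PD, NE and PD, and its footnote adds that "non-CR/non-PD is preferred over SD for nontarget disease". The same appendix defines SD among the target-lesion criteria, as shrinkage too small for PR "nor sufficient increase to qualify for PD, taking as reference the smallest sum diameters while on study".

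The two documents describe the general rule differently. Protocol 9.4.3.1: "Participants known to be alive and without disease progression will be censored at the last known date of progression-free assessment". SAP 4.3.1: "Participants known to be alive and without disease progression will be censored according to the censoring scheme detailed in Section 4.3.2".

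**The concern.** The footnote is a closed list, and the response category that Appendix 3 assigns to a stable nontarget-only patient is not on it. Such a patient could have a year of clean, on-schedule scans and still be treated as having no post-baseline assessment. That conflicts with the narrative sentence in the same Protocol section.

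This scheme sets the censoring date for all three primary PFS hypotheses, and BIRC PFS uses the same methods. Resetting event-free patients to day 1 discards follow-up. It takes more from the arm with more event-free patients, so it pulls the HR toward 1 and costs power. The clinical benefit rate has a parallel gap: it counts SD of at least 24 weeks but not non-CR/non-PD of that length, while these patients stay in the denominator.

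**Working it through.** **Tracing one patient.** Take a patient with non-measurable bone-only disease, scanned on schedule, with no progression, no death and no nontarget CR.

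1. Table 3 rates every post-baseline scan non-CR/non-PD.
2. Footnote b does not list that rating, so no post-baseline scan is adequate.
3. The event-free row therefore gives randomization. The new-therapy row gives the same date if treatment is switched before PD.
4. The Protocol 9.4.3.1 sentence gives the date of the last clean scan instead.

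The death row, whose condition is no adequate post-baseline assessment "available and death reported after 2 scan intervals", would catch a death without PD in the same way. SA3 restores that event. No sensitivity analysis restores the event-free date: SA1 and SA2 still use the last adequate assessment, and SA3 and SA4 deal only with PD or death.

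**Who is affected.** Only patients rated under Table 3. Appendix 3 treats a lytic or mixed bone lesion with a measurable soft-tissue component as measurable. Those patients have target lesions, use Table 2 and can be SD.

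**The plan's power, reproduced.** Power = Φ(√(D/4)·|ln HR| − z₁₋α).

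- H1: √(480/4) × |ln 0.74| − 2.576 = 3.298 − 2.576 = 0.722, giving 76.5% (stated: at least 76%).
- H2: √(192/4) × |ln 0.57| − 2.054 = 3.894 − 2.054 = 1.840, giving 96.7% (stated: about 97%).
- H3: √(248/4) × |ln 0.70| − 1.960 = 2.808 − 1.960 = 0.848, giving 80.2% (stated: at least 80%).

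**Patients reset.** The documents give neither the share of non-measurable bone-only disease nor PFS in that group. I assume shares of 10/20/30%, planned PFS in the group and no nontarget CR. Event-free patients at the final analysis, times share:

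- H1: 640 − 480 = 160, so 16/32/48. The reset fraction is 25% overall, about 29% in Arm A and 21% in Arm B.
- H2: 240 − 192 = 48, so 5/10/14.
- H3: 440 − 248 = 192, so 19/38/58.

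If 10% of the event-free patients in this group have a nontarget CR, the reset fraction falls from 25% to about 22% (H1) and from 44% to about 39% (H3).

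**Effect on the tests.** Simulation, 20,000 runs per setting (Monte Carlo error about 0.3 points). It uses SAP Section 5 accrual, exponential PFS at the planned medians, scans every 8 weeks to week 56 and then every 12 weeks, and an unstratified log-rank test. There are no deaths without PD and no new therapy before PD. All PDs are kept, so event counts do not change. Both censoring dates are applied to the same data. HRs come from 400,000 simulated patients per comparison.

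| | Last scan | Reset, 10/20/30% share |
|---|---|---|
| H1 power at 0.005 | 76% | 73/69/65% |
| H1 power at 0.019 (after H2 is rejected) | 89% | 87/84/82% |
| H2 power at 0.02 | about 97% | 96/94/93% |
| H3 power at 0.025 | 80% | 77/74/71% |
| H1 overall HR | 0.740 | 0.746/0.752/0.759 |
| H3 overall HR | 0.698 | 0.705/0.714/0.723 |

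If median PFS in this group is 1.5 times the planned value, H1 power goes from 76/74/74% to 73/68/64% and H3 from 79/79/78% to 78/76/72%.

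**Clinical benefit rate.** Understatement = share × proportion progression-free at 24 weeks (5.52 months). That proportion is 0.5^(5.52/4.3) = 41% in Arm B, 0.5^(5.52/5.8) = 52% in Arm A and 0.5^(5.52/8.3) = 63% in Arm C. The rate is understated by about 4/8/12, 5/10/16 and 6/13/19 points respectively.

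**The case against.** The strongest reply is that the intent is clear. The SAP's rationale for its intercurrent-event strategies (Section 1.1) explains this censoring by scheduled assessments that did not take place, so that progression may have gone unseen. A bone-only patient scanned on time does not fit that description. The Protocol sentence and the dedicated bone-only progression rule point the same way. The Table 3 footnote says non-CR/non-PD is preferred over SD, which can be read as two labels for one state, and footnote b may be shorthand for evaluable as against NE. If sites or the programming record SD, nothing changes.

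Most of this stands: the last scan was very probably intended. But neither document states the mapping, Table 3 has no SD row, Appendix 3 ties SD to target-lesion diameters, and the SAP defers to the table. A literal program would produce the wrong date.

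A reader might infer more than the documents support:

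- *That late progressions are lost too.* Footnote c could be read to censor PD after about day 120 (2 × 56 + 8). The row concerned requires missing scans, and these scans were done. No figure above uses that reading.
- *That the prespecified bone-only subgroup is distorted by a known amount.* SAP 4.8.1 derives nature of disease from target and nontarget lesion locations, so the subgroup in SAP 4.8.12 may include measurable patients who are unaffected.
- *That the Kaplan-Meier curve for these patients must fall to zero.* This needs every one of them to lack a nontarget CR. In simulation, their 12-month PFS in Arm C, 40% as planned, falls to 6% with no CR, 10% if 10% of the event-free patients have CR and 18% if 30% do.

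**Conclusion.** The point holds as a wording error in the primary-endpoint censoring rule. Taken literally, footnote b contradicts the Protocol's own text and the SAP's rationale, and it censors at randomization patients who were followed as planned. It reaches only non-measurable bone-only disease without a nontarget CR.

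The direction is conservative, and nothing here suggests inflation of type I error. If the literal rule were programmed, the overall HR would move by about 0.01 to 0.03. Power would fall by about 3 to 11 points for H1 at its initial alpha (76% to 73/69/65%) and 3 to 9 points for H3 (80% to 77/74/71%). These sizes rest on assumed shares of 10/20/30%, planned PFS in the group, no nontarget CR and retention of all PDs. If SD is recorded, or the Protocol sentence is followed, the effect is nil. The contradiction in the text does not depend on any of these assumptions. The clinical benefit rate gap is real but matters less, because that endpoint is not error-controlled.

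**What to change.** In footnote b of the PFS censoring table, in both SAP 4.3.2 and Protocol 9.4.3.1, list the adequate responses as *CR, PR, SD, non-CR/non-PD, or PD*. In the clinical benefit rate definition, in SAP 4.4.2 and Protocol 9.4.3.3, count *SD or non-CR/non-PD ≥ 24 weeks*. Make both edits before database lock, and check that the analysis programs follow them.

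The cost is one phrase in each place. No event target, alpha level, data collection or patient procedure changes. If the sponsor already intends the last scan, the edit simply records that.
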